## 5.

# STUDY SYNOPSIS **Study Title** An assessment of the impact of **CONT**rast **EN**hance**D** Spectral Mammography (CESM) on patient management and comparison with MRI (CONTEND Study) Internal ref. no. RADIOL/2015/CONTEND **Study Design** The aim of this pilot study is to establish the Contrast Enhanced Spectral Mammography (CESM) technique and study procedures. Results of this pilot and feedback from staff will inform Phase 2 of the study which will be a larger, multi-centre, randomised control trial. The study will be undertaken by members of the Cambridge Breast Unit (CBU) at Addenbrooke's Hospital, Cambridge using CESM technology provided by GE Healthcare as an upgrade to the GE Senographe Essential digital mammography system. This technology is already established throughout the world and has FDA approval and is CE marked. This will be a randomised, sequential cohort study. Following standard mammography and ultrasound all women with lesions of suspicion 3, 4 or 5 will be randomised to either receive CESM in addition to their assessment procedure or to receive usual care. Sealed envelopes will be held at CBU reception desk containing either 'CESM' or 'Usual Care' and one will be selected at random to determine to which arm of the study the woman is allocated. After providing informed consent, those women randomised to receive CESM will undergo the procedure either during the same clinic visit or on a day following the initial clinic visit. This will be dependent upon clinic time and staff availability and the woman's own preferences / circumstances. The index lesion and any additional disease detected by CESM will be biopsied as appropriate and results will be discussed at the multidisciplinary meeting (MDT). For those with biopsy confirmed disease a decision will be made at that meeting regarding conservation surgery, mastectomy or neo-adjuvant therapy. For those with benign disease

confirmed by core biopsy standard care will be followed.

MRI will be performed on appropriate women in line with standard practice. Additional disease detected by MRI will be biopsied if this will influence patient management. Biopsies will be undertaken using either ultrasound or MRI guidance. These cases will be discussed at the MDT and a decision made regarding conservation surgery, mastectomy or neo-adjuvant therapy.

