The pathway for women randomised to receive usual care will be the same as for those randomised to receive CESM, excluding the CESM procedure, i.e. they will undergo biopsy during their initial clinic visit and results will be discussed at the MDT where a decision regarding their future management will be made.

A flowchart illustrating patient pathways during the CONTEND Study can be found in Appendix I of this document.

A proforma will be used for each case to record patient pathway, results of biopsies and MDT patient management decisions.

Staff will be asked to provide feedback on patient acceptability and ease of undertaking the CESM procedure. They will also be asked to record any incidents of note, e.g. patient related problems; impact on clinic; issues with equipment. Time taken to undertake the examination will be recorded.

In order to compare the diagnostic accuracy of CESM with MRI, CESM images and MRI images will be anonymised and read by different readers - CESM images will be reported without the knowledge of the MRI results and vice versa. Mammography and ultrasound images will be available. A completed report on a proforma will be the basis for statistical analysis.

Histopathology data collected following surgery or from core biopsy if surgery is not undertaken and will be used as the gold standard for measurement of tumour size and extent of disease. If the patient is having primary drug therapy, tumour size will be determined from the mammogram.

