Two studies which do directly compare the diagnostic accuracy of CESM with MRI have been reported recently. Jochelson et al studied 52 patients, measuring maximum diameter of the index (main) tumour on imaging (9). Of the 52 lesions, conventional mammography detected 42 and both MRI and CESM detected 50. CESM was accurate for tumour extent in all but 2 index lesions, whereas MRI gave accurate size estimation for all. Jochelson et al concluded that CESM detected known primary tumours at a rate comparable to that of MRI (both 96%) and higher than that of conventional digital mammography (81%). CESM had a lower sensitivity (56%) for detecting additional cancers than MRI (88%), but the specificity was higher. On the other hand MRI found 13 false positive cases, 8 having surgery for ultimately benign change, whereas CESM found 2 false positives, not requiring surgery.

In the second study, Fallenberg et al also reported on the detection of breast cancer and tumour size assessment for CESM compared with MRI (10). They studied 80 patients with newly diagnosed breast cancer of which there was post-op histology for 59. Images were reviewed by an independent reader blinded to other findings. All index tumours (100%) were detected by CESM, 77 (97.4%) by MRI and 66 (82.5%) by conventional mammography. In the correlation of tumour size measurements, there were significant differences between both CESM and MRI compared to mammography. Between CESM and MRI there was no significant difference observed. The best correlation was between CESM and histopathology. There was no evaluation of additional lesions reported.

CESM is a developing technology and the optimum design of equipment and mechanism is still under debate. The addition of digital breast tomosynthesis (DBT) to CESM should further enhance the performance of CESM compared to MRI. Schmitzberger et al (2011) successfully demonstrated the clinical feasibility of CESM DBT as a diagnostic tool but stated

further studies were needed to assess diagnostic sensitivity and specificity (11).

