# 8.2 Primary and Secondary Endpoints/Outcome Measures

The primary endpoint is the detection of additional disease that changes patient management. Analysis will be undertaken to determine the impact of CESM on patient management decisions (actual or hypothetical). These will be extracted from details recorded on the proforma.

Secondary endpoints are the sensitivity and specificity of CESM and MRI on a per lesion basis - including comparison of the maximum dimension of the index tumour - as assessed by independent readers and compared with surgical histopathology. The efficacy of each technique at detecting additional lesions and the number of false positives identified by each will also be determined.

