# 10.2 Analysis of Endpoints

Data from all eligible subjects will be included in the analyses. These will be patients for whom we have data from MRI, CESM and surgical histopathology.

Statistical significance of differences between CESM and MRI will be calculated using McNemar's test . Receiver operating characteristic (ROC) curves will be constructed for both imaging modalities.

Agreement between maximum lesion diameter based on CESM and MRI or CESM and histopathology will be expressed in Bland-Altman plots.

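### Accuracy is judged per lesion against surgical histopathology, so a finding that was biopsied but not excised in an operated woman has a recorded result that the stated reference does not use

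*Protocol*

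**What the plan says.** Protocol section 8.2 fixes the unit of analysis: "Secondary endpoints are the sensitivity and specificity of CESM and MRI on a per lesion basis". The same sentence fixes the comparator: "as assessed by independent readers and compared with surgical histopathology". The secondary endpoint entry in section 5 (Study Synopsis) and the Analysis paragraph of section 8.4 repeat both.

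The study design part of the synopsis adds a second source: "Histopathology data collected following surgery or from core biopsy if surgery is not undertaken and will be used as the gold standard". The sentence goes on to say what that standard is for; it is the "gold standard for measurement of tumour size and extent of disease".

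Section 10.2 defines the analysis set: "These will be patients for whom we have data from MRI, CESM and surgical histopathology".

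On biopsy, the synopsis says of CESM: "The index lesion and any additional disease detected by CESM will be biopsied as appropriate". Of MRI it says: "Additional disease detected by MRI will be biopsied if this will influence patient management". Biopsy results go on the case proforma.

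The secondary endpoint entry of the synopsis also says that false positives are to be verified by follow-up at 6 months. Sections 8.2, 8.4 and 10.2 do not mention this. Section 8.1 (Trial duration) ends participation once CESM is done, and section 8.4.2 ends the study when the last patient's surgical histopathology is available.

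**The concern.** The endpoint is counted lesion by lesion, but the natural reading of the reference rule works woman by woman: surgical histopathology if she had surgery, core biopsy if she did not. In a woman operated on for her index tumour, a second focus or a contralateral finding may have been sampled and left in place. Its result is on the proforma, yet the stated comparator for sensitivity and specificity does not reach it.

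These lesions matter to the study. Section 7.2 lists additional lesions, contralateral lesions and false positives as parts of the accuracy comparison. The Rationale hopes to show higher sensitivity and specificity than MRI and will use the results for power calculations in a larger trial. Specificity needs lesions that are negative on the reference, and a surgical reference is most easily missing for benign lesions left in place. Without a stated rule, two analysts could obtain different specificities from the same data.

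**Working it through.** **1. Which lesions have a stated reference for benign or malignant status?** Reading sections 5, 8.2, 8.4 and 10.2 together:

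- Index lesion excised: surgical histopathology.
- Additional ipsilateral finding inside a mastectomy specimen: surgical histopathology.
- Additional finding in an operated woman, biopsied, site not excised (outside a conservation specimen, or contralateral): core histology is recorded but no stated rule uses it.
- Additional finding never biopsied or excised: only the 6-month follow-up in the synopsis, for the false-positive count.
- Any finding in a woman with no surgery: core biopsy is allowed by the synopsis, but section 10.2 leaves her out of the set. Read per woman, the biopsy exception reaches nobody in that set.

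**2. Direction of the effect.** The protocol does not say how the third group is handled.

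- If dropped, benign findings leave the false-positive count of the modality that reported them, and its specificity is too high. Where the other modality was negative, it loses a true negative, and McNemar's test loses a discordant pair.
- If scored as not confirmed at surgery, benign ones are rightly counted as false positives. A finding malignant on core, but not excised or with no residual tumour in the specimen, is wrongly counted as one. Specificity is then too low and a true positive is lost.

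**3. Illustration of the first case.** The protocol gives no figure of its own here. The Summary of literature (section 6) cites a 52-patient comparison whose detection rates reproduce: 50/52 = 96% and 42/52 = 81%. It reports: "MRI found 13 false positive cases, 8 having surgery for ultimately benign change, whereas CESM found 2 false positives, not requiring surgery".

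Assume one case is one finding, that those without surgery are exactly those without surgical histology, and that they are dropped.

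- MRI: 13 counted on all evidence, 8 on surgical histology alone; 13 − 8 = 5 lost, 5/13 = 38%.
- CESM: 2 counted on all evidence, 0 on surgical histology alone; 2 − 0 = 2 lost, 2/2 = 100%.
- Gap, MRI minus CESM: 13 − 2 = 11 becomes 8 − 0 = 8.
- Exact 95% intervals for the share lost: MRI 14% to 68%, CESM 16% to 100%. Fisher's exact test comparing the shares: p = 0.20.
- Exact McNemar on false positives (pairing not reported): all evidence, p = 0.007 with no overlap (13 v 2) or p = 0.001 if both CESM findings are shared with MRI (11 v 0). Surgical only, 8 v 0, p = 0.008.

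The protocol quotes no true-negative counts, so specificity itself cannot be computed.

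**4. Scale in this trial.** The number of CESM women who will also have MRI and surgery is not given. Assume 20% to 100% of 50, so n = 10 to 50, with the cited rates per woman.

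- MRI false positives: n × 13/52 = 2.5 to 12.5 expected; n × 8/52 = 1.5 to 7.7 seen on surgical histology alone.
- CESM false positives: n × 2/52 = 0.4 to 1.9 expected; 0 seen.

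**The case against.** A reader might infer that the plan hides false positives, CESM's most of all, and drives CESM specificity to 100% by construction. The documents do not support that, for three reasons.

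- The synopsis gives false positives a verification route at 6 months that needs no excision. In both the synopsis and section 8.2 their number stands in a sentence of its own, not tied to surgical histopathology. Loss of false positives from that count is therefore not established.
- Nothing says that unexcised findings are dropped. They could equally be scored as unconfirmed, which leaves the direction open.
- The claim about CESM rests on two findings in one cited study. It holds for the share lost (2/2 v 5/13) but not for the number lost (2 v 5), and the gap in CESM's favour narrows. The different biopsy triggers for CESM and MRI findings might produce unequal losses here, but no rates are given.

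Other points also have force. Section 10.2 selects women, not lesions, and does not expressly bar an operated woman's other biopsy results. The synopsis condition about surgery has no stated subject and could be read per lesion. Its sentence concerns size and extent, not benign or malignant status. These are secondary endpoints of a single-centre pilot, and lesion-level detail may sit in an SAP that was not available.

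What remains is that the protocol does fix a reference, in three places, as surgical histopathology. Even the per-lesion reading of the synopsis sentence does not change the comparator named in section 8.2. The 6-month follow-up is not linked to specificity, and it fits poorly with the ends of participation and of study in sections 8.1 and 8.4.2.

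**Conclusion.** The point stands as a mismatch between a per-lesion endpoint and its stated reference. A biopsied, unexcised additional or contralateral finding in an operated woman has a recorded histology that the reference for sensitivity and specificity does not use. The 6-month confirmation is not carried into the sections that define and analyse the endpoints. The possible bias in specificity has no fixed sign. The 8 v 0 against 13 v 2 contrast shows what dropping such findings could do if the cited pattern held; it does not predict this trial. The problem is confined to sites outside the surgical specimen and to secondary endpoints. It is worth correcting because the pilot's accuracy estimates are meant to inform the next trial.

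**What to change.** In sections 8.2, 8.4 and 10.2, and in the synopsis, define benign or malignant status per lesion, in this order:

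1. surgical histopathology of that site, if excised;
2. otherwise core biopsy of that site;
3. otherwise the 6-month follow-up already named in the synopsis.

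State that a malignant core stands even if no residual tumour is found at surgery. Say in section 10.2 that lesions with any of these references enter the per-lesion analysis. Leave the reference for size and extent as a separate matter. Reconcile the 6-month follow-up with the end of participation in section 8.1 and the end of study in section 8.4.2.

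The cost is mainly wording, since biopsy results are already on the proforma; follow-up data need a place in the data collection. The downside is a mixed reference, because a benign core or a short follow-up can miss cancer. Report the number of lesions resting on each source, by modality, and give an analysis on surgical histology alone as a sensitivity check.

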# **Study Participants**

Women attending CBU who have lesions of suspicion 3, 4 or 5 following routine mammography and ultrasound.

50 patients with successful CESM examinations will be required to establish the technique, study procedures and to provide sufficient data to inform further study. It is estimated, due to randomisation procedure, approximately 100 patients will need to be recruited in order to obtain this number.
Recruitment to the study is planned to run for 12 months or until sufficient number of participants has been accrued. The study will end once data analysis is complete.
To assess the impact the addition of CESM has on patient management.
To compare the sensitivity and specificity of CESM with MRI.
The detection of additional disease by CESM that changes patient management. Analysis will be undertaken to determine the impact of CESM on patient management decisions (actual or hypothetical). These will be extracted from details recorded on the proforma.
Secondary endpoints are the sensitivity and specificity of CESM and MRI on a per lesion basis – including comparison of the maximum dimension of the index tumour – as assessed by independent readers and compared with surgical histopathology.
The efficacy of each technique at detecting additional lesions and the number of false positives identified by each will also be determined. False positives will be confirmed through follow up at 6 months.
Analysis of results will inform further study, e.g. sample size and power calculations, and will include an assessment of clinical technique and study procedures from staff questionnaires.

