### 7.2 Secondary objectives

To compare the sensitivity and specificity of CESM with MRI. Analysis will include:

- index lesion size
- detection of additional lesions
- detection of lesions in contralateral breast
- total extent of disease
- number of false positives identified

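### Absolute sensitivity for additional and contralateral lesions has no reference standard in image-negative, unremoved tissue, so it is biased upward by an amount the protocol cannot fix

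*Protocol*

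**What the plan says.** - **Endpoint and reference standard.** Section 8.2, the Synopsis (section 5) and the Analysis paragraph of section 8.4 all set per-lesion sensitivity and specificity "as assessed by independent readers and compared with surgical histopathology".
- **Scope.** Section 7.2 lists, under the comparison of sensitivity and specificity, additional lesions, total extent of disease and "detection of lesions in contralateral breast". Section 8.2 adds: "The efficacy of each technique at detecting additional lesions and the number of false positives identified by each will also be determined".
- **Treatment paths.** In the Synopsis, the choice at the multidisciplinary meeting is "regarding conservation surgery, mastectomy or neo-adjuvant therapy", so part or all of a breast may stay in place.
- **Biopsy.** The Synopsis says "The index lesion and any additional disease detected by CESM will be biopsied as appropriate". For additional disease found by MRI it uses a different condition, namely that the result would affect management.
- **Other references.** When there is no operation, histology comes "from core biopsy if surgery is not undertaken and will be used as the gold standard for measurement of tumour size and extent of disease". The Synopsis also says: "False positives will be confirmed through follow up at 6 months".
- **Closing points.** Under Trial duration (section 8.1), a woman's participation ends after CESM. Under section 8.4.2, the study ends when the last patient's surgical histology is available.
- **Analysis set.** Section 10.2 requires MRI, CESM and surgical histology for each patient, not for each breast or region. McNemar's test is the only test named.

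**The concern.** Surgical histology describes only the tissue that was removed. After conservation surgery it says nothing about the rest of that breast, and in a woman operated on one side it says nothing about the other, although CESM takes views of both. In that tissue a cancer becomes known only if some examination showed it and it was then biopsied or excised. A cancer that nothing showed is not scored as a miss. It is simply absent from the list of lesions.

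A sensitivity whose denominator leaves out the shared misses can only be too high. The pilot is meant to inform the sample size and power of a multicentre comparison of CESM with MRI (Synopsis; Rationale in section 6). A single absolute figure for additional or contralateral disease, passed on without qualification, would carry this bias into that design.

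**Working it through.** **The plan's own figure.** The only planning number is about 100 participants to give 50 with CESM (section 10.1). With equal allocation, 50 / 0.5 = 100, so it reproduces. It does not bear on this point. The protocol states no expected sensitivity for its own patients and no rate of conservation surgery or occult disease.

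**Is there any reference for image-negative tissue?**
- Surgical histology covers removed tissue only.
- Core biopsy is aimed at the index lesion and at disease already seen, and the fallback is stated for tumour size and extent.
- Six-month follow-up is stated for false positives only, and appears in the Synopsis but not in section 8.2.
- Participation ends after CESM and the study ends at the last surgical histology, so no later search for missed cancers is planned.
- The analysis set in section 10.2 works per patient, so unexamined regions of included women remain in the comparison.

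None of these covers tissue that looked clear and was left in place.

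**Size, as an illustration.** Inputs: S = 0.56 (CESM) and 0.88 (MRI), which the Summary of literature in section 6 cites for additional cancers. Treating them as true values is an assumption. Let b be the share of cancers missed by both and u the share of those that never reach histology. If all detected cancers are confirmed,

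apparent sensitivity = S / (1 − u·b).

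The documents give neither b nor u, but b is bounded:
- smallest: 0, since 0.44 + 0.12 is below 1
- independent misses: 0.44 × 0.12 = 0.0528
- largest (CESM finds nothing that MRI misses): min(0.44, 0.12) = 0.12

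| b | u | CESM | MRI | Difference (points) | Ratio |
|---|---|---|---|---|---|
| 0 | any | 56.0% | 88.0% | 32.0 | 0.636 |
| 0.0528 | 0.5 | 0.56/0.9736 = 57.5% | 0.88/0.9736 = 90.4% | 32.9 | 0.636 |
| 0.0528 | 1 | 0.56/0.9472 = 59.1% | 0.88/0.9472 = 92.9% | 33.8 | 0.636 |
| 0.12 | 0.5 | 0.56/0.94 = 59.6% | 0.88/0.94 = 93.6% | 34.0 | 0.636 |
| 0.12 | 1 | 0.56/0.88 = 63.6% | 0.88/0.88 = 100% | 36.4 | 0.636 |

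Both sensitivities are inflated by the same factor, 1 / (1 − u·b), so the shift in percentage points is larger for MRI.

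**What is not affected.** Per 100 true cancers with independent misses:
- found by both: 49.28
- CESM only: 6.72
- MRI only: 38.72
- neither: 5.28

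McNemar's test uses only 6.72 and 38.72. The ratio is (49.28 + 6.72) / (49.28 + 38.72) = 56 / 88 = 0.636. Neither uses the last cell, which is the one that goes missing.

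**Does restriction to removed tissue cure it?** Not fully. Tissue tends to be removed because imaging showed disease there. If every detected cancer is excised and a share 1 − u of the doubly missed ones happens to lie in specimens, the restricted estimate is again S / (1 − u·b).

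**The case against.** The strongest case against the point has five parts.

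1. **Section 8.2 promises less than absolute sensitivity for additional lesions.** It puts them in a separate sentence about the efficacy of each technique, and the only named test is McNemar's, which doubly missed lesions do not disturb. The remark about the test stands. However, section 7.2 places additional and contralateral lesions expressly under sensitivity and specificity, so absolute figures for them are within the plan.

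2. **Denominator rules belong in a statistical analysis plan, which is not shown.** In general that is fair. Here the protocol itself fixes both the reference standard and the scope, and the two do not fit together.

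3. **Some missed cancers will still be found.** Every woman has mammography and ultrasound first, a specimen can reveal a cancer that both modalities missed, and an excised contralateral lesion does have histology. All of this stands. A reader might infer that cancers missed by CESM and MRI are never counted, or that MRI must come out at 100%. The documents do not support either. The figure of 100% needs complete nesting of detections and no doubly missed cancer confirmed by any route.

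4. **The size is hypothetical.** This stands. A reader might take the share of breasts without surgery as a measure of the bias. It is not one, because the bias depends on how many cancers lie there, which the protocol does not say. With independent misses and half of them verified, the shift is 1.5 points for CESM and 2.4 for MRI.

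5. **The ratio is not automatically sound.** This also stands. It is immune to doubly missed lesions, but it assumes that CESM-marked and MRI-marked lesions are confirmed alike, and the Synopsis words the two biopsy conditions differently.

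**Conclusion.** The point holds for absolute sensitivity for additional and contralateral lesions. The protocol measures it against surgical histology, includes tissue that usually has none, and gives no substitute where imaging was negative. The bias can only be upward, and it vanishes only if no cancer is missed by both modalities or every such cancer reaches histology.

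Its size cannot be fixed from the documents. Taking the cited 56% and 88% as true and all detected cancers as confirmed, the reported values could lie anywhere in 56.0–63.6% for CESM and 88.0–100% for MRI, with the difference growing from 32.0 to at most 36.4 points.

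It would go too far to conclude that the CESM–MRI comparison fails. Doubly missed lesions leave the ratio of 0.636 and McNemar's discordant pairs unchanged. Nor does the protocol say that the absolute figure for these lesions will be the Phase 2 input. It says only that the results will inform sample size and power. This is a secondary endpoint of a pilot. The change is worth making because it is cheap and alters what the pilot may claim.

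**What to change.** In sections 8.2 and 10.2:

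1. For additional and contralateral lesions, make the main result the paired relative detection: the CESM/MRI ratio among histologically confirmed lesions, with a confidence interval that allows for several lesions in one woman. Give the counts found by each modality beside it.
2. State that the ratio assumes CESM-marked and MRI-marked lesions are verified alike. The differing biopsy wording in the Synopsis must be reconciled. Which wording should apply is not a statistical question.
3. Report absolute sensitivity only for lesions in surgically removed tissue, counting an excised contralateral lesion as removed tissue. Label it as conditional on verified tissue and probably still too high, because excision follows imaging findings.
4. Give the Phase 2 sample-size calculation the relative figure, or a range for the absolute one, not a single absolute value.

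The cost is some analysis wording and one location field on the proforma (inside the specimen, outside it, or contralateral). The price is that fewer lesions stand behind any absolute sensitivity, in a study with about 50 CESM examinations and fewer women who also have MRI and surgery.
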